#### **11.5 Analysis of Safety Endpoints**

Safety measures including adverse events, clinical laboratory tests, vital signs, and concomitant medication usage will be summarized descriptively by treatment group.

The principle of treatment emergence will be employed for the analysis of adverse event data. A treatment-emergent adverse event is defined to be any event that occurs during the observation period of the study and was not present at baseline, or exacerbation of a condition present at baseline.

Treatment-emergent adverse events will be classified by the Medical Dictionary for Regulatory Activities. The type, incidence, timing (onset, duration), relationship, and severity will be reported for all adverse events. Reasons for withdrawal due to adverse events will also be reported.

#### **11.6 Sample Size Calculations**

The following table summarizes the RBT-9 advantages (15-18%) that can be detected with 84-85% power and 252 subjects for a 2-sided hypothesis test with 5% overall Type 1 error with 2-sided 4.5% Type 1 error remaining at the final analysis; this alpha spend accounts for the preplanned interim analyses.

Two group  $\chi^2$  test: Null hypothesis is Equal Failure %s (odds ratio = 1)

	84-85% Power			Two-sided p=0.045		
	1	2	3	1	2	3
Test significance level, $\alpha$	0.045	0.045	0.045	0.045	0.045	0.045
1 or 2-sided test?	2	2	2	2	2	2
Placebo Failure %, $\pi_1$	25%	32%	38%	25%	32%	38%
RBT Failure %, $\pi_2$	10%	15%	20%	14.6%	20.4%	25.7%
Odds ratio, $\pi_2(1-\pi_1)/[\pi_1(1-\pi_2)]$	0.333	0.375	0.408	0.513	0.545	0.564
Power (%)	84	85	84	NA	NA	NA
Placebo sample size, n1	84	84	84	84	84	84
RBT sample size, n2	168	168	168	168	168	168
Ratio: n2 / n1	2	2	2	2	2	2
N = n1 + n2	252	252	252	252	252	252

## 11.7 Interim Analysis

A group sequential design will be conducted with 3 pre-planned interim analyses after 30, 60, and 90 subjects complete the Day 7 evaluation and once 150 subjects complete the Day 28 evaluation. At each interim, the DSMB will evaluate an independently conducted analysis in order to assess safety and futility.

The interim analyses will be subject to adaptations according to Cui; 2-sided 0.1% alpha at the second interim and 2-sided 0.2% alpha at each of the third and fourth interim analyses. Enrollment will be stopped if the conditional power is <10% based on the percentage of subjects classified in categories 4 through 8 on the 8-point WHO Ordinal Clinical Scale for RBT-9 versus placebo.

For the second, third, and fourth interim analyses, the conditional power will be assessed. Futility will be declared if the conditional power is <10%, while efficacy will be declared at the fourth interim analysis if the conditional power is >80% (with all subjects followed through Day 28); sample size re-estimation will be performed to increase the sample size to 252 subjects. Enrollment will be recommended if futility is observed. If efficacy is declared, the DSMB will advise regarding study continuation.

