#### **9.3.1 Stopping Rules**

For the second, third, and fourth interim analysis, the primary endpoint will be assessed for futility by the DSMB. Enrollment will be stopped if the conditional power is  $<10\%$  based on the percentage of subjects classified in categories 4 through 8 on the 8-point WHO Ordinal Clinical Scale for RBT-9 versus placebo.

Efficacy will be declared at the fourth interim analysis if the conditional power is  $>80\%$  (with all subjects followed through Day 28). If efficacy is declared, the DSMB will advise regarding study continuation.

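### Alpha is assigned to interims 2 and 3, which have only a futility rule, and the interim 4 efficacy claim is not tied to its 0.2%, so the stated 5% overall error is not what the rules deliver

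*Combined protocol and SAP*

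**What the plan says.** Section 11.7 schedules the looks "after 30, 60, and 90 subjects complete the Day 7 evaluation and once 150 subjects complete the Day 28 evaluation" and assigns them "2-sided 0.1% alpha at the second interim and 2-sided 0.2% alpha at each of the third and fourth interim analyses". No level is given for the first look. Section 11.6 states "5% overall Type 1 error with 2-sided 4.5% Type 1 error remaining at the final analysis" and adds that "this alpha spend accounts for the preplanned interim analyses".

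The decision rules are written separately from these levels. Sections 9.3.1 and 11.7 and the synopsis stop enrollment at interims 2, 3 and 4 if conditional power is below 10%. The only efficacy rule is that "efficacy will be declared at the fourth interim analysis if the conditional power is >80" per cent. Section 11.7 describes the purpose of the looks in general as follows: "At each interim, the DSMB will evaluate an independently conducted analysis in order to assess safety and futility". The synopsis labels the looks at 60 and 90 subjects as safety and efficacy, with futility in parentheses.

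Nowhere does the protocol say what the 0.1% and 0.2% are compared with, or how the 0.2% at interim 4 relates to the 80% conditional power threshold.

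**The concern.** An alpha level has meaning only when a rejection decision is attached to it. A futility stop cannot produce a false efficacy claim, so it needs no alpha. As written, 0.3% is deducted from the final test for two looks with no efficacy decision, and the remainder was found by subtraction, which ignores the correlation between successive looks. Both features make the final test slightly stricter than a 5% overall error requires.

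Interim 4 raises the opposite and larger problem. It has an alpha level and an efficacy rule, but the rule does not use the level. If conditional power above 80% is enough for a claim, the effective boundary is far looser than 0.2%. What is at stake is whether the 5% overall error stated in section 11.6 and the synopsis is true, and in which direction it is wrong.

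**Working it through.** **Inputs.** Interim levels 0.001, 0.002 and 0.002 (section 11.7). Final level 0.045 and overall 0.05 (section 11.6). Look sizes 60, 90, 150 and 252 (sections 11.6 and 11.7). Groups of 84 and 168, with failure rates 25/10%, 32/15% and 38/20% (section 11.6). Assumptions: normal approximation, information proportional to sample size with 252 as the final size, and non-binding futility.

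**1. The plan's own figures.** 0.1 + 0.2 + 0.2 + 4.5 = 5.0, so the 4.5% is a plain additive remainder. The pooled chi-square test at 0.045 gives power of 84.9, 85.6 and 84.6%, in line with the tabled 84, 85 and 84%. Sections 11.3 and 11.4 name Fisher's exact test for the primary endpoint; by exact enumeration its power is 83.6, 84.0 and 82.5%.

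**2. Overall error if the levels are p-value boundaries.** Overall error = 1 − P(all |Z_i| < c_i), with Z multivariate normal and corr(Z_i, Z_j) = √(n_i/n_j). The critical values are 3.291 (0.1%), 3.090 (0.2%) and 2.005 (4.5%).

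- Interim 4 and final only: correlation √(150/252) = 0.772, overall error **4.54%**.
- All three interim levels and final: **4.67%**. Interims 2 and 3 use Day 7 data, so their correlation with the Day 28 looks is unknown. Multiplying it by r gives 4.67% at r = 1 and 4.79% at r = 0.

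**3. Overall error if conditional power is the claim.** Under the current trend, CP = Φ[(Z/√t − 2.005)/√(1 − t)], with t = 150/252 = 0.595. Setting CP = 0.80:

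Z = √t × (2.005 + 0.842 × √(1 − t)) = 0.772 × (2.005 + 0.842 × 0.636) = **1.96**

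This is a nominal two-sided p of 0.050. The 0.2% level needs Z = 3.09, where CP is 99.9%. A boundary of 1.96 at interim 4 followed by a final test at 4.5% gives an overall two-sided error of **7.6%**, or about 6.1% if only interim 4 crossings favouring RBT-9 count. If conditional power is instead computed under the design effects, the threshold falls to Z of about 1.64 to 1.68, which is looser still.

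**4. Final level that restores 5%.**

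| Looks that can claim efficacy | Additive | From joint distribution |
|---|---|---|
| Interim 4 at 0.2%, final | 4.8% | 4.966%, so 4.96% rounded down |
| Interims 2, 3 and 4, final | 4.5% | 4.71% (r = 0) to 4.83% (r = 1) |

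Checks: in the first row, 4.96% gives 4.994% overall and 4.97% gives 5.004%, so the level should be rounded down. In the second row, 4.83% gives about 5.1% at r = 0 or 0.5, while 4.7% stays below 5% throughout.

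**5. What the change buys.** Fisher power moves from 83.57 to 84.04%, from 84.00 to 84.72%, and from 82.49 to 83.47% when the final level goes from 4.5% to 4.96%. The gains are 0.47, 0.72 and 0.98 points.

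**6. Raising the final level alone.** With the conditional power rule left as the claim and its threshold recomputed for the new final level, overall error rises from 7.6% to about 8.2% at 4.96% and 8.3% at 4.97%.

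**The case against.** A reader might infer that the protocol forbids an efficacy claim at interims 2 and 3, so that their alpha can never be used. The text does not go that far. It writes no efficacy rule for those looks, but it does assign them test levels, and the synopsis label mentions efficacy. An efficacy boundary may have been intended and left unwritten, or the 0.3% may be a deliberate penalty for unblinded comparative looks. The supportable statement is that the purpose of this alpha is not given.

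An additive split is also valid. It needs no assumption about correlation, which is an advantage here because the Day 7 and Day 28 looks measure status at different times. Retaining a slightly conservative final level in a Phase 2 trial is a legitimate choice, and the tabled power is already reproduced by the test that the table names. The loss is therefore minor.

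Finally, section 11 defers full detail to a separate statistical analysis plan, and the Cui weights and boundaries may be set there. That could resolve the ambiguity, but the protocol itself states both the 5% figure and the interim 4 efficacy rule, and these two have to agree.

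**Conclusion.** The point holds as a small correction. The 4.5% does not correspond to a 5% overall error under either reading of interim 4: the error is about 4.54% if the claim there requires p<0.002, and about 7.6% if conditional power above 80% suffices.

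Two stronger readings should be resisted. One is that the design is simply conservative and the final level can be raised safely; this is true only once interim 4 is held to 0.2%. The other is that the trial's error is 7.6%. That figure depends on treating the crossing as the efficacy claim and on conditional power under the current trend, neither of which the protocol spells out.

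The unused alpha is worth at most about one power point, or roughly 6 to 9 subjects of 252 on the chi-square calculation. The figures rest on final information at 252 and non-binding futility. The value of the change lies mainly in making the stated 5% true.

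**What to change.** Adopt these together:

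1. In sections 9.3.1 and 11.7 and the synopsis, let efficacy be claimed at interim 4 only if the two-sided p-value is below 0.002. Conditional power may still guide futility and sample size, but must not by itself support a claim.
2. Remove the alpha from interims 2 and 3 and state that they can stop enrollment for futility only.
3. In section 11.6 and the synopsis, set the final level from the joint distribution at 150/252, about 4.96%, using the same pre-specified weights as the Cui method. If an additive split is preferred, use 4.8%. Rerun the power table at the chosen level.

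If efficacy stopping at interims 2 and 3 is intended, write the boundaries out and keep the final level at no more than about 4.7%, because the Day 7 to Day 28 correlation is unknown. Change 1 is still needed.

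Do not make change 3 without change 1.

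The cost is a few sentences and numbers in three sections and the synopsis, with matching text in the analysis plan. No subjects are added. The one real consequence is that an early claim at interim 4 needs Z of 3.09 rather than about 1.96, which is what the stated 0.2% already implies.

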The interim analyses will be subject to adaptations according to Cui; 2-sided 0.1% alpha at the second (n=60) interim and 2-sided 0.2% alpha at each of the third (n=90) and fourth (n=150) interim analyses. Enrollment will be stopped for futility if the conditional power is <10% based on the percentage of subjects classified in categories 4 through 8 on the 8-point WHO Ordinal Clinical Scale for RBT-9 versus placebo. Enrollment will be recommended if futility is observed. Efficacy will be declared if the conditional power is >80% at the fourth interim analysis; the DSMB will advise regarding study continuation.

**Sample Size Estimate:** The following table summarizes the RBT-9 advantages (15-18%) that can be detected with 84-85% power and 252 subjects for a 2-sided hypothesis test with 5% overall Type 1 error with 2-sided 4.5% Type 1 error remaining at the final analysis; this alpha spend accounts for the preplanned interim analyses.

Two group  $\chi^2$  test: Null hypothesis is Equal Failure %s (odds ratio = 1)

	84-85% Power			Two-sided p=0.045		
	1	2	3	1	2	3
Test significance level, $\alpha$	0.045	0.045	0.045	0.045	0.045	0.045
1 or 2-sided test?	2	2	2	2	2	2
Placebo Failure %, $\pi_1$	25%	32%	38%	25%	32%	38%
RBT Failure %, $\pi_2$	10%	15%	20%	14.6%	20.4%	25.7%
Odds ratio, $\pi_2(1-\pi_1)/[\pi_1(1-\pi_2)]$	0.333	0.375	0.408	0.513	0.545	0.564
Power (%)	84	85	84	NA	NA	NA
Placebo sample size, n1	84	84	84	84	84	84
RBT sample size, n2	168	168	168	168	168	168
Ratio: n2 / n1	2	2	2	2	2	2
N = n1 + n2	252	252	252	252	252	252

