### **9.3 Study Design**

This is a Phase 2, randomized, placebo-controlled, multicenter study that will evaluate the efficacy, tolerability, and safety of a single dose of RBT-9 on the progression of COVID-19 infection in non-critically ill adults who are at high risk due to age and/or comorbid conditions. Subjects with documented SARS-CoV-2 infection who are at high risk for disease progression, as defined in the inclusion criteria (see [Section 9.1](#)), and require observation and/or treatment in a hospital will be screened for entry into the study. Eligible subjects will be stratified by time since COVID-19 diagnosis (<48 hours,  $\geq$ 48 hours) and randomly assigned in a 2:1 ratio to receive a single intravenous infusion of 90 mg RBT-9 or placebo (normal saline). No more than 24 hours can elapse between Screening and Dosing of RBT-9.

All subjects will be assessed through Day 56. All subjects, regardless of hospitalization status, will be assessed on Days 7, 14, 21, and 28, according to the Event Schedule (see [Section 5.1](#)). Assessments will include severity of COVID-19 measured by the 8-point WHO Ordinal Clinical Scale, physical examination, vital signs, clinical laboratory evaluations, concomitant medications, and adverse events. For subjects who have been discharged from the hospital, visits on Days 7, 14, and 21 will be conducted virtually (eg, by telephone or video contact). The Day 28 visit should be conducted in person, but may be conducted virtually, as well. Subjects will also be assessed at safety follow-up visits, which will be conducted virtually (eg, by telephone or video contact) on Days 42 and 56.

An independent data and safety monitoring board (DSMB) will actively monitor interim data to make recommendations regarding study conduct/continuation. The DSMB will meet once the first 30 subjects complete the Day 7 assessment to perform the first interim analysis of the safety data. Enrollment of 30 additional subjects will proceed if the safety profile of RBT-9 is deemed acceptable (as determined by the DSMB). Two additional DSMB interim analyses will be performed once 60 and 90 subjects complete the Day 7 evaluation. The last DSMB interim analysis will be performed once 150 subjects complete the Day 28 evaluation; sample size re-estimation will also be performed to allow a sample size increase to 252 subjects based on pre-defined conditional power rules.

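### The 84-85% power leaves out the conditional-power futility stops, whose convention these documents do not state, and one sentence reverses the stopping rule

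*Combined protocol and SAP*

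**What the plan says.** Section 11.6, repeated in the synopsis, gives "RBT-9 advantages (15-18%) that can be detected with 84-85% power and 252 subjects". The table is for a two-group chi-square test with 84 placebo and 168 RBT-9 subjects at two-sided 0.045. On the interim looks it says only that "this alpha spend accounts for the preplanned interim analyses".

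The futility rule appears in three places. Section 9.3.1: "For the second, third, and fourth interim analysis, the primary endpoint will be assessed for futility by the DSMB". Section 11.7: "Enrollment will be stopped if the conditional power is <10% based on the percentage of subjects classified in categories 4 through 8". The synopsis: "Enrollment will be stopped for futility if the conditional power is <10"%. The looks are at 60 and 90 subjects with Day 7 data, and at 150 subjects with Day 28 data.

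Three other statements bear on how the rule works:

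- Section 9.3 says the DSMB "will actively monitor interim data to make recommendations regarding study conduct/continuation", which is advisory wording beside the flat instruction to stop.
- Section 9.3 also says "sample size re-estimation will also be performed to allow a sample size increase to 252 subjects based on pre-defined conditional power rules". Those rules are not given here, and Section 11 defers detail to a separate SAP that is not available for this review.
- Section 11.7 and the synopsis both say "Enrollment will be recommended if futility is observed".

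**The concern.** A futility stop can end a trial of a drug that works, so it can only lower power relative to the same design without it. Protecting the Type 1 error at the interim looks does nothing to recover that loss. A power figure computed as if there were one look therefore needs either a futility rule that costs almost nothing or a stated allowance.

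How much a 10% conditional-power rule costs depends on the effect assumed for subjects not yet observed. At 60 of 252 subjects most of the information is still to come, so that assumption dominates the result. The same interim table can stop the trial under one convention and leave it comfortably running under another. A DSMB working from these pages could not tell which applies, and would also meet a sentence that points the opposite way when futility is found.

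**Working it through.** **Inputs.** From Section 11.6: failure rates of 25 v 10%, 32 v 15% and 38 v 20%; 84 and 168 subjects; final two-sided alpha 0.045 (critical Z 2.005). From Section 11.7: interim alpha 0.001, 0.002 and 0.002 at 60, 90 and 150 subjects; futility if conditional power is below 10%.

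**Step 1: reproduce the stated power.** Power = Φ[(d − 2.005·s0)/s1], where d is the difference in failure rates, s0 the pooled standard error and s1 the unpooled one. For 25 v 10%: d = 0.15, pooled rate 0.15, s0 = √(0.15 × 0.85 × (1/84 + 1/168)) = 0.0477, s1 = √(0.25 × 0.75/84 + 0.10 × 0.90/168) = 0.0526. This gives (0.15 − 0.0957)/0.0526 = 1.03, or 84.9%. The other scenarios give 85.6% and 84.6%, against a stated 84, 85 and 84%. The figure is single-look power. The alpha split adds up: 0.001 + 0.002 + 0.002 + 0.045 = 0.050. Neither step contains a futility term.

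**Step 2: conditional power under two conventions.** With t = n/252, CP = Φ[(Z√t + θ(1 − t) − 2.005)/√(1 − t)]. Under the planned effect θ = d/s0 = 3.144, 3.142 or 3.071 by scenario. Under the observed trend θ = Z/√t.

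Worked case at n = 60, with 6/20 placebo and 10/40 RBT-9 failures: Z = 0.05/√(0.267 × 0.733 × (1/20 + 1/40)) = 0.41 and t = 0.238.

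- Observed trend: (0.202 + 0.645 − 2.005)/0.873 = −1.33, so CP = 9%.
- Planned effect (θ = 3.144): (0.202 + 2.395 − 2.005)/0.873 = 0.68, so CP = 75%.

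| Look | Placebo v RBT-9 failures | CP, observed trend | CP, planned effect |
|---|---|---|---|
| 60 | 6/20 v 10/40 | 9.2% | 73-75% |
| 90 | 9/30 v 15/60 | 7.4% | 63-65% |
| 150 | 16/50 v 25/100 | 9.6% | 46-48% |

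In each row the observed trend stops the trial and the planned effect does not. In terms of Z, the observed-trend rule stops below 0.43, 0.58 and 0.92 at the three looks. The planned-effect rule stops below about −3.1, −1.7 and −0.1.

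**Step 3: power with the rule included.** Binomial simulation with 600,000 trials per scenario, 2:1 allocation, pooled Z and the stated efficacy alphas. It assumes a final N of 252, every stop followed, and interim failure rates equal to the Day 28 rates.

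| Futility rule | 25 v 10 | 32 v 15 | 38 v 20 |
|---|---|---|---|
| None | 85.8% | 86.2% | 85.0% |
| Planned effect, all three looks | 85.8% | 86.2% | 84.9% |
| Observed trend, all three looks | 73.7% | 74.4% | 72.6% |
| Observed trend, n = 150 only | 83.5% | 83.9% | 82.7% |

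With the observed trend at all looks, 20.3, 19.8 and 21.2% of trials with the planned effect stop for futility. Of all trials, 14.7, 14.0 and 15.4% stop at n = 60. Power is 84 − 73.7 = 10.3, 85 − 74.4 = 10.6 and 84 − 72.6 = 11.4 points below the stated figures.

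**Step 4: how far Day 7 timing moves this.** The documents give no Day 7 rates, so both cases are assumptions, run with the observed trend at all looks.

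- Weaker signal (only 90, 70 or 50% of failures visible by Day 7, equally in both arms): power is 70-72%, 64-66% or 55-57%.
- Stronger signal (Day 7 rates of 40 v 16, 50 v 23.5 and 55 v 29%): power is 81.0, 81.5 and 79.6%.

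**Step 5: the planned test.** The primary test is Fisher exact, not chi-square. With planned-effect futility at N = 252 it gives 83.9, 84.2 and 82.6%. The drop from Step 3 (1.9, 2.0 and 2.3 points) comes from the test, not from the futility rule.

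**The case against.** The strongest reply is that no shortfall has been shown. The projection convention, the projected N and the binding status are ordinary SAP content, Section 11 defers to a SAP, and Section 9.3 refers to pre-defined conditional power rules. Under the planned effect the futility rule costs almost nothing. If the DSMB only recommends, some stops would be overruled and the loss would shrink. All of this stands, and it limits the finding to what these documents can support. It does not remove it: the protocol prints both the power and the stopping rule, and they should agree there.

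A reader might infer that the trial has at most about 73-74% power. The documents do not support that. Subjects on oxygen can enroll and the scale records status on a given day, so the Day 7 signal may be stronger or weaker than the Day 28 signal. Step 4 moves power both ways.

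A reader might equally infer that choosing the planned effect guarantees 84-85%. That is not established either. The third scenario is about 82.6% with the Fisher test. The synopsis also calls 252 a maximum, and it is reached by a re-estimation that the simulation does not model.

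The reversed sentence may well be a dropped word, since the stop is stated plainly elsewhere. It still appears twice, in the text a DSMB would consult.

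**Conclusion.** The point holds. The stated power is a single-look figure with no allowance for three futility checks, and these documents do not fix the convention that decides whether the omission matters. Under the Step 3 assumptions the cost is negligible with the planned effect and about 10 to 11 points below the stated power with the observed trend. That range is illustrative, because it depends on Day 7 rates the documents do not give and on how often the DSMB follows the rule. The contradiction between recommending and stopping enrollment needs no assumption: it is there on the page in both the synopsis and Section 11.7. Both matters should be fixed.

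**What to change.** 1. Reconcile the sentence on recommending enrollment with the stopping rule, in Section 11.7 and in the synopsis.
2. In the same two places, state that futility conditional power is computed under the planned effect and projected to 252. The alternative is to use the observed trend only at 150 subjects, the one look with Day 28 data. That gives about 83-84% with pooled Z, and the Fisher test would be expected to lower it further.
3. State whether the stop is binding or advisory.
4. Restate power from a simulation that includes the futility rule, the Day 7 timing, the re-estimation and the Fisher exact test. At N = 252 with the planned effect, and before Day 7 timing and re-estimation are added, expect about 83-84%, with the third scenario slightly below its stated 84%.

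**Cost.** Wording and a small simulation, with no extra subjects. The real downside is slower stopping of an ineffective drug. With no true difference, about 48% of trials stop by 150 subjects under the planned effect, against about 88% with the observed trend at all looks. Under the alternative in item 2, such a trial normally runs to 150 subjects, where 81-82% stop. The published power may also become slightly less favourable.

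### At the fourth interim, efficacy is declared on conditional power above 80% (met at p of about 0.05 under the current trend and N = 252), yet that look is allotted only 0.2% alpha

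*Combined protocol and SAP*

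**What the plan says.** Two rules apply to the same look, the analysis of 150 subjects with Day 28 data.

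- **Conditional power rule.** Section 11.7: "efficacy will be declared at the fourth interim analysis if the conditional power is >80% (with all subjects followed through Day 28"). The Synopsis (Section 4, Interim Analyses) has the same: "Efficacy will be declared if the conditional power is >80% at the fourth interim analysis". Section 9.3.1 repeats it: "Efficacy will be declared at the fourth interim analysis if the conditional power is" above 80%.
- **Alpha allotment.** Section 11.7 gives "2-sided 0.1% alpha at the second interim and 2-sided 0.2% alpha at each of the third and fourth interim analyses". The Synopsis attaches sample sizes: "2-sided 0.2% alpha at each of the third (n=90) and fourth (n=150) interim analyses".

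Section 11.6 plans for "5% overall Type 1 error with 2-sided 4.5% Type 1 error remaining at the final analysis" and says that this spend accounts for the interim looks.

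Conditional power has two other uses. Section 11.7: "Futility will be declared if the conditional power is <10"%. Section 9.3: "sample size re-estimation will also be performed to allow a sample size increase to 252 subjects based on pre-defined conditional power rules". The protocol does not state the drift assumed for conditional power, the test behind it, the sample size before the increase, or whether the futility stops are binding.

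**The concern.** Conditional power above 80% is a forecast that the final test would succeed if the study continued. It is not a test at the alpha set aside for the current look. The protocol's alpha budget adds up only if each look is tested at its allotted level, yet the sentence that triggers an efficacy claim at n = 150 uses the forecast.

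The same data can therefore be a declared efficacy result under one sentence and short of significance under another. The DSMB and the sponsor would have to choose between them with unblinded results in hand. The choice also decides whether the stated 5% overall Type 1 error is met.

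**Working it through.** **Inputs.** Fourth look at n = 150, maximum N = 252, 2:1 allocation (84 placebo, 168 RBT-9), final 2-sided alpha 0.045, interim alphas 0.001, 0.002 and 0.002 (Sections 11.6 and 11.7; Synopsis). Current-trend conditional power is an assumption.

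**The plan's own figures.** The alphas add up: 0.1 + 0.2 + 0.2 + 4.5 = 5.0%. A two-proportion power calculation with 84 and 168 subjects at 2-sided 0.045 gives 84.9%, 85.6% and 84.6% for the three scenarios, against the 84%, 85% and 84% printed. So the inputs are read correctly.

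**Where conditional power reaches 80%.** Under the current trend,

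CP = Φ[(Z/√t − c)/√(1 − t)], with t = 150/252 = 0.595 and c = 2.0047 (2-sided 0.045).

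Setting CP = 0.80:

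Z = √t × [c + 0.8416 × √(1 − t)] = 0.7715 × (2.0047 + 0.8416 × 0.6362) = 0.7715 × 2.5401 = 1.960, so p = 0.050.

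The allotted boundary is Z = 3.090 (p = 0.002), where CP = Φ[(3.090/0.7715 − 2.0047)/0.6362] = 99.9%. In p-value terms the efficacy rule is about 25 times looser (0.050/0.002). With 32% failures on placebo and 50 and 100 subjects, the conditional power rule is met at an RBT-9 failure rate of about 17.8%. The 0.2% boundary needs about 11.3%.

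**Sensitivity to what is not stated.**

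- Final N of 160 to 220 instead of 252: p = 0.031 to 0.041 at the threshold.
- Planned-effect drift: Z = 1.72 to 1.80 (p about 0.07 to 0.09), looser still. The range reflects drift set from 84% power (2.999) or from the three tabulated scenarios (2.85 to 2.94).
- Null drift: Z = 3.29 (p = 0.001), slightly stricter than 0.2%. But the 10% futility rule on that basis would stop 64% of trials at n = 60 under the planned effect, which does not fit a design claiming 84-85% power.

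**Type 1 error.** Simulated normal paths with independent increments; looks at 60, 90, 150 and N; the allotted alphas elsewhere; the conditional power rule on the benefit side only; futility at current-trend CP below 10%. The Day 7 looks at 60 and 90 are treated as measuring the primary endpoint and may claim efficacy at their allotted alphas.

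| Setting | Fourth look on CP > 80% | Fourth look on p ≤ 0.002 |
|---|---|---|
| N = 252, chi-square, non-binding | 3.84 (benefit) + 2.33 (harm) = 6.2% | 4.7% |
| N = 252, chi-square, binding | 3.01 + 0.05 = 3.1% | 1.70 + 0.05 = 1.75% |
| N = 252, Fisher, non-binding | 5.0-5.2% | 3.9-4.0% |
| N = 252, Fisher, binding | 2.3-2.5% | 1.3-1.5% |

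The Fisher rows are binomial simulations at null failure rates of 25%, 32% and 38%. If the conditional power rule were applied in both directions, the first entry would be 7.7%. With only the n = 150 and final looks it is 6.1%. For a pre-increase N of 160, 180, 200 or 220 (chi-square), the non-binding totals are 4.8, 5.1, 5.4 and 5.7%, and the benefit-side error under binding futility is 2.0, 2.2, 2.4 and 2.6%.

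**An example with the planned test.** Take 16/50 failures on placebo and 16/100 on RBT-9. Fisher's exact test gives p = 0.034. Drawing the remaining 34 (84 − 50) and 68 (168 − 100) subjects at the observed rates gives a conditional power of about 89% for Fisher p ≤ 0.045 at the end, so efficacy is declared. With 16/50 on placebo, p ≤ 0.002 needs 10/100 or fewer failures on RBT-9.

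**The case against.** The strongest reply is that a breach of 5% is not established. The 6.2% needs chi-square, N = 252, current-trend conditional power and non-binding futility together, and the protocol leans away from some of these. Sections 9.3.1 and 11.7 say that enrolment will be stopped for futility, which reads as binding (although Section 11.7 also has a sentence that, as worded, recommends enrolment when futility is seen). The planned primary test is Fisher's exact test. An increase to 252 implies a smaller starting N. Under binding futility every total above is below 5%. The 2.5% benchmark for one direction is a convention, not a limit set in the protocol. This stands: the excess over 5% is conditional and has to be reported with its conditions.

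The treatment of Day 7 looks as if they measured the Day 28 endpoint also affects the absolute power levels. This stands too, but the Type 1 error barely moves (6.1% with only the fourth and final looks), and neither does the power lost to the fix.

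Other replies are weaker. Section 11 defers detail to a separate SAP, which is not among the documents reviewed; but the protocol itself states the decision rule three times, and further detail cannot undo a conflict in the rule. The method of Cui is only named; it deals with a change of sample size, not with an efficacy claim on conditional power. The DSMB's advice concerns continuation after efficacy has been declared, so the declaration itself is not advisory.

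**Conclusion.** The concern holds. The protocol gives the fourth interim two efficacy criteria and does not say which governs. The contradiction does not depend on how conditional power is computed. Under the current trend and under the planned effect, the conditional power rule is much looser than the allotted 0.2% (p of about 0.03 to 0.09 over the sample sizes and drifts tried). Only null drift brings the two close, and that reading fits poorly with the futility rule.

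For error control at N = 252, the 5% total is exceeded with chi-square and non-binding futility (6.2%), is about reached with Fisher and non-binding futility (5.0-5.2%), and is respected with binding futility. Even then, with chi-square, the chance of a false claim of benefit is 3.0% rather than 1.7%. As the binding status, the starting N, the test and the drift are all unstated, the 5% in Section 11.6 cannot be confirmed from the text. This decides whether a positive result is declared on the primary endpoint, so it must be settled before the fourth interim.

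**What to change.** In Section 11.7, Section 9.3.1 and the Synopsis, declare efficacy at the fourth interim only if the primary test gives 2-sided p ≤ 0.002, the alpha already allotted. Use conditional power only for futility and sample size re-estimation. If conditional power is above 80% but p exceeds 0.002, continue to the final analysis. State the drift and test used for conditional power, the N before re-estimation, and whether the futility stops are binding.

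The cost is wording in three places and fewer early claims. Under the planned effect, with futility stops at all three looks and N = 252, claims made at n = 150 fall from about 50% to 14% (cumulatively through that look, from about 60% to 24%). Overall power falls from 74.0% to 72.3%, or 1.7 points. With only the n = 150 and final looks, the levels are 84% and 82%, so the loss is again about 2 points.

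If the sponsor prefers to claim efficacy on conditional power, the alternative is to re-derive the interim and final alphas for that rule and show that the overall error stays at 5%.
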